##### **EM is defined as:**

- $< 15$  headache days of which at least 4 or more headache days meet criteria as migraine days during the baseline period based on the eDiary calculations

After signing the informed consent form, subjects will enter the screening period. The screening period includes a screening period (up to 3 weeks) followed by a 4-week baseline period. At the day 1 visit (window is +7 consecutive calendar days; the day 1 visit must occur 28 to 35 days after the week -4 baseline period visit date), eligible subjects will be randomized into the 12-week double-blind treatment period and will begin to receive double-blind investigational product. At the week 10 visit, subjects will receive the last dose of treatment with investigational product. At the week 12 visit, subjects will end the double-blind treatment period. A safety follow-up period will be conducted 18 weeks after the last dose of investigational product (16 weeks after the end of the double-blind treatment period). Subjects will use an eDiary every day throughout the baseline period, double-blind treatment period, and safety follow-up period to report information about the migraine and non-migraine headaches and acute medication use. Subjects will have in-clinic study visits Q2W after day 1 through to the week 12 visit and then Q4W.

The overall study design is described by a study schema in [Section 2.1](#). The endpoints are defined in [Section 4.1](#).

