5.1 Endpoints

5.1.1 Efficacy Endpoints

The baseline period for efficacy analysis is defined as the period between week -4 visit (date on which the eDiary device is set up) and the day prior to study day 1 (study day 1 is not included).

eDiary Day

A day in which a subject uses the eDiary and data are entered for that day.

Migraine Day

A migraine day is any calendar day from the eDiary in which the subject experiences a qualified migraine headache (onset, continuation or recurrence of the migraine headache). A qualified migraine headache is defined as a migraine with or without aura, lasting for ≥ 4 hours, and meeting at least one of the following criteria:

- a) ≥ 2 of the following pain features:
 - Unilateral
 - Throbbing
 - Moderate to severe
 - Exacerbated with exercise/physical activity
- b) ≥ 1 of the following associated symptoms:
 - Nausea and/or vomiting
 - Photophobia and phonophobia

If the subject took a migraine-specific medication (ie, triptan or ergotamine) during aura or to treat headache on a calendar day, then it will be counted as a migraine day regardless of the duration and pain features/associated symptoms.

Monthly Migraine Days

Number of migraine days during a 28-day period. Monthly migraine days at baseline are the number of migraine days in the baseline period. Days without eDiary data in each monthly interval are handled by proration according to [Section 8.3](#).

Headache Day

A headache day is any calendar day from the eDiary in which the subject experiences a qualified headache (initial onset, continuation or recurrence of the headache). A qualified headache is defined as:

- a qualified migraine headache (including an aura-only event that is treated with acute migraine-specific medication), or
- a qualified non-migraine headache, which is a headache that lasts ≥ 4 hours and is not a qualified migraine headache, or
- A headache of any duration for which acute headache treatment is administered.

Monthly Headache Days

Number of headache days during a 28-day period. Monthly headache days at baseline are the number of headache days in baseline period. Days without eDiary data in each monthly interval are handled by proration according to [Section 8.3](#).

Information Day

A day which is either a headache day or an eDiary day.

Migraine Attack

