A migraine attack is an episode of any qualified migraine headache or migraine specific medication intakes for aura only. The following rules will be used to distinguish an attack of long duration from two attacks, or to distinguish between attacks and relapses:

- a) A migraine attack that is interrupted by sleep, or temporarily remits, and then recurs within 48 hours will be considered as one attack and not two.
- b) An attack treated successfully with medication but with relapse within 48 hours will be considered as one attack.

A migraine attack lasting more than 48 hours will be counted as one attack.

Monthly Migraine Attacks

Number of migraine attacks during each 28-day period. Monthly migraine attacks at baseline are the number of migraine attacks in baseline period. Days without eDiary data are handled by proration according to Section 8.3.

Response

At least a 50% (or at least 75% or 100%) reduction from baseline in monthly migraine days over the last 4 weeks of the DBTP.

Monthly Acute Headache Medication Treatment Days

Number of days on which acute headache medications are used as recorded in eDiary during each 28-day period. Monthly acute headache medication treatment days at baseline are the number of acute headache medication treatment days in the baseline period. Days without eDiary data are handled by proration according to [Section 8.3](#).

Monthly Acute Migraine-specific Medication Treatment Days

Number of days on which migraine specific medications are used during each 28-day period. Migraine-specific medications include two categories of medications: triptan-based migraine medications and ergotamine-based migraine medications. Monthly migraine-specific medication treatment days at baseline are the number of migraine-specific medication treatment days in the baseline period. Days without eDiary data are handled by proration according to Section 8.3.

Monthly Average Severity of Migraine Pain

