5.4 Study Time Intervals

Monthly Interval for Efficacy Endpoints

Monthly efficacy measurements will be calculated based on the 2-week IP dosing schedule defined below using eDiary data collected from the beginning of the baseline phase (week -4 visit) up to the end of the safety follow-up phase (week 28 end of eDiary use). Any eDiary data occurring after EOS date or after the end date of the last monthly interval defined below, whichever comes earlier, will not be included in the analysis.

Table 5-1. Monthly Interval for Efficacy Endpoints Derived From Daily eDiary Data

Study Phase	Assessment Time Point	Monthly Interval	
		Start Date/Day	End Date/Day
Baseline Phase	Baseline	eDiary device assignment date (week -4 visit)	The day of or prior to Study Day 1
Double-blind Treatment Phase	Week 4	Study Day 1	
• Week 4 dose date – 1• Else MIN(Study Day 28, EOS) if Week 4 dose was not received
	Week 8	
• Week 4 dose date• Else Study Day 29 if Week 4 dose was not received	
• Week 8 dose date – 1• Else MIN(Study Day 56, EOS) if Week 8 dose was not received
	Week 12	
• Week 8 dose date• Else Study Day 57 if Week 8 dose was not received	
• MIN(Study Day 84, EOS)
Safety Follow-up Period	Week 16	
• Study Day 85	
• MIN(Study Day 112, EOS)
	Week 20	
• Study Day 113	
• MIN(Study Day 140, EOS)
	Week 24	
• Study Day 141	
• MIN(Study Day 168, EOS)
	Week 28	
• Study Day 169	
• MIN(Study Day 196, EOS)

Study Visit

Since the actual visit for a subject may not exactly coincide with their targeted visit date, the actual visit date is mapped to the study visit as following. The study day window will be utilized to define study visit for lab, vital signs, physical measurements and PROs collected during office visits including HIT-6, and MMIDAS. Any data occurring after the EOS date will not be included in the analysis with the exception of lab shift analyses and antibody data.

Table 5-2. Study Visit Windows for HIT-6, MMIDAS, C-SSRS, and CAPS Scale

Study Phase	Study Visit	Target Day	Study Day

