- **Prior use of anti-CGRP medication (yes, no)**
- **Prior migraine prophylactic treatment failures (1, \geq 2)**
- **Medication overuse (yes, no)**
- **CAPS score (0, \geq 1)**
- **Age (< median, \geq median)**
- **Sex (female, male)**
- **Race (White, Other)**
- **Response status to AMG 334 (yes, no)**

The purpose of the subgroup analyses is to explore if the treatment effect varies across subgroups of interest. Subgroup analyses are performed for primary efficacy endpoint using the same method as primary analysis method but performed within each interested subgroup. The treatment difference (or odds ratio) with associated 95% confidence intervals and p-values will be reported within each subgroup.

Note: if the subgroup is one of the stratification factors, the stratification factor will not be included in the model, but the other randomized stratum will be included (ie, if the subgroup is prophylactic migraine medication, then randomized region would be included in the model instead of randomized strata which combined both stratification factors). **These subgroups will be re-examined for appropriateness and may be re-categorized (due to small sample size, for example, if there are < 10% of subjects within a subgroup) before unblinding. The analyses of these subgroups will be exploratory in nature.**

The heterogeneity of the treatment effect across the subgroups will be evaluated for the primary endpoints by examining the treatment by subgroup interaction and a p-value will be presented. For continuous endpoints, the primary analysis model with the addition of treatment group by subgroup interaction will be used.

Primary summary and analysis method with treatment and stratification interaction for continuous endpoints: the interaction of treatment group by stratification variable will be tested with significant level of 0.15. If the interaction term is significant, the interaction term will be included in the model as sensitivity analysis for the primary analysis method.

Time from last dose of study drug to loss of response will be evaluated during the Safety Follow-up period. For responders, loss of response is defined as the first time the subject returns to < 50% reduction from the baseline period in monthly migraine days. For non-responders, loss of response will be evaluated by

percentage of reduction from the baseline period in monthly migraine days over time.

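### SAP 9.5.1 dates loss of response to one follow-up month below 50% reduction, so a substantial share of Week 12 responders would be called lost with no waning

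*SAP*

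**What the plan says.** - **What is timed.** SAP 9.5.1: "Time from last dose of study drug to loss of response will be evaluated during the Safety Follow-up period". Under Protocol 5.1, "At the week 10 visit, subjects will receive the last dose of treatment", which falls inside the month that defines response.
- **Who is a responder.** SAP 5.1.1 defines response as at least a 50% "reduction from baseline in monthly migraine days over the last 4 weeks of the DBTP". The unit is "Number of migraine days during a 28-day period", so response rests on one monthly count set against the baseline count.
- **When response is lost.** SAP 9.5.1, on the monthly count of migraine days: "For responders, loss of response is defined as the first time the subject returns to < 50% reduction from the baseline period in monthly migraine". No second month is needed to confirm it.
- **How many looks.** SAP 5.4, Table 5-1, sets four follow-up intervals: Weeks 16, 20, 24 and 28 (Days 85-112, 113-140, 141-168 and 169-196).
- **Non-responders.** "For non-responders, loss of response will be evaluated by" their percentage reduction from baseline over time.
- **What is not stated for this analysis.** There is no censoring rule, estimator or contrast between arms. SAP 9.1 does require summary statistics by treatment group.
- **Scope.** SAP Section 13 lists follow-up efficacy data as outside the plan, apart from the change in headache days from Week 12 to Week 16. That conflicts with 9.5.1.

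**The concern.** A subject enters the responder group because one variable monthly count was at most half of another. Some cross that line partly by chance and tend to move back. The rule then takes the first of four further single-month counts that exceeds half of baseline as the date of loss. Selection on a favourable month and repeated unconfirmed looks both push towards early loss, even if nothing about the treatment effect changes.

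At stake is the description of how long benefit lasts after the last dose. With the rule as written, a reader cannot tell how much of a short time to loss is waning and how much is monthly variation. Responders are also a post-randomization subset, so the amount of regression to the mean can differ between arms. Setting AMG 301 responders beside placebo responders is then not a randomized comparison.

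**Working it through.** The plan states no figure for loss of response, and its sample-size inputs are redacted, so there is nothing to reproduce. Taken from the documents: the one-month rule, selection on Weeks 9-12, and four looks (16 weeks = 112 days; 112/28 = 4, as in Table 5-1). Response rate, month-to-month correlation and count variability are assumptions. In every calculation below the response rate in the arm stays constant after Week 12.

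**1. Independent months.** If q is the chance that a Week 12 responder stays at or above 50% reduction in any one follow-up month, P(called lost) = 1 - q^4.
- q = 0.7: 1 - 0.2401 = 76%
- q = 0.8: 1 - 0.4096 = 59%
- q = 0.9: 1 - 0.6561 = 34%

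The share exceeds one half whenever q is below 0.5^(1/4) = 0.841.

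**2. Correlated months.** Five months (Week 12 plus four) follow a latent Gaussian with correlation rho, a constant monthly responder rate, and conditioning on response at Week 12. SAP 9.5.1 names an AR(1) structure for the treatment-period model but gives no rho. Percent called lost:

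| Structure, rho | rate 20% | 30% | 40% | 50% |
|---|---|---|---|---|
| Exchangeable 0.5 | 88 | 82 | 75 | 67 |
| Exchangeable 0.7 | 74 | 66 | 59 | 51 |
| Exchangeable 0.8 | 63 | 55 | 49 | 42 |
| Exchangeable 0.9 | 47 | 40 | 35 | 29 |
| Exchangeable 0.95 | 34 | 29 | 25 | 21 |
| AR(1) 0.5 | 96 | 91 | 86 | 78 |
| AR(1) 0.7 | 87 | 80 | 72 | 64 |
| AR(1) 0.8 | 77 | 69 | 62 | 54 |
| AR(1) 0.9 | 60 | 52 | 45 | 39 |
| AR(1) 0.95 | 45 | 38 | 33 | 28 |

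Under AR(1) individual levels drift while the arm stays level, so part of that loss is real individual change. The exchangeable rows have no such drift.

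**3. Simulated 28-day counts.** Assumed: CM:EM 50:50; true baseline means 17 (CM) and 8.5 (EM) days, SD 3.5 and 2.2; the entry limits applied; a permanent subject-level on-treatment/baseline ratio with mean 0.6-0.8 and SD 0.15-0.35; binomial counts or counts overdispersed up to 2.5-fold. This gave 27 settings.
- No waning: 43-92% of responders are called lost.
- Responders whose true reduction is at least 50% and permanent: 27-72% are called lost.
- Complete waning by the third follow-up month: 98-100% are called lost. The rule therefore separates none from complete by only 6-56 percentage points.
- Two consecutive months required: about 20-63% are called lost with no waning. Separation rises to 24-74 points and is better in all 27 settings.

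Under the Gaussian model, the two-month rule still fires without waning in 12-23% (exchangeable, rho 0.9) to 46-79% (AR(1), rho 0.5). Confirmation reduces the artefact and does not remove it.

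**4. Missing months.** SAP 8.3.4 carries treatment-period handling into follow-up. If non-responder imputation were applied here, missing months alone would flag 1 - 0.98^4 = 8% of responders at 2% missing per month, and 1 - 0.95^4 = 19% at 5%.

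**The case against.** **Size.** A reader might infer that most Week 12 responders would be called lost with no waning. The documents do not support that. It needs the responder rate and the month-to-month correlation, and neither is given. With exchangeable rho of 0.9 or more, the share stays below half at every responder rate tried. In the count model with binomial counts and ratio SD 0.35 it is about 43%, 50% and 57% at mean ratios 0.6, 0.7 and 0.8. This limits the size; no setting gave a negligible share.

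**Placebo.** It is also tempting to say that there is no placebo reference and that the result could not be interpreted. SAP 9.1 calls for summaries by treatment group, Protocol Table 7-1 counts placebo as investigational product, and nothing in 9.5.1 limits the analysis to AMG 301. Placebo responders would be displayed and give a partial benchmark. What stands is that no contrast is specified and that the responder subsets are not randomized groups.

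**Non-responders.** The sentence could be read as applying a loss event to people with no response to lose. It goes on to describe percentage reduction over time, which is a sensible summary under an unsuitable label.

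**Time to event.** The planned quantity is a time, and comparing only the share ever lost by month four understates what timing can show. This is true but modest. At mean ratio 0.7, SD 0.25 and 2.5-fold overdispersion, separation is 28 points at month two (59% against 87%) and 23 at month four.

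**Importance.** The analysis is descriptive, with no alpha, hypothesis or decision rule, and no visible objective names durability. Section 13 may exclude it altogether. That lowers the priority, but the text in 9.5.1 still has to change or go.

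**Conclusion.** The point holds in limited form. SAP 9.5.1 sets a rule that calls a substantial share of Week 12 responders lost when the arm's response is not waning: about 20-60% at very high month-to-month correlation (0.9 or more) and about 50-95% at moderate correlation (up to about 0.7 exchangeable, 0.8 AR(1)). These ranges rest on assumed responder rates of 20-50% and assumed correlations. The direction, towards short durability in every arm, was the same in every setting tried. Primary and secondary conclusions are untouched, so this is a minor to moderate correction that should be made before unblinding.

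**What to change.** 1. Reconcile SAP 9.5.1 with Section 13. If follow-up efficacy is out of scope, delete the loss-of-response paragraph. If it is kept, make changes 2 to 4.
2. Make the main durability summary the AMG 301 minus placebo difference in change in monthly migraine days at Weeks 16, 20, 24 and 28, with 95% confidence intervals, in all PAS subjects as randomized. The mixed model in 9.5.1 uses only the 12-week treatment-period data, so it must be extended to the follow-up intervals in Table 5-1. Fit this as a separate model so that the Week 12 primary result stays as planned.
3. Date loss of response to the first of two consecutive months with less than 50% reduction, and show placebo responders beside each AMG 301 arm. Keep the single-month rule as a sensitivity summary.
4. Keep the non-responder summary of percentage reduction over time, but do not call it loss of response.

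**Cost.** SAP wording, one extra model and one extra table, from diary data already collected through Week 28; no new visits. A first drop at Week 28 cannot be confirmed and is censored. The two-month rule also detects somewhat less true waning: under complete waning it fires in roughly 80-94% of responders, depending on the assumed spread, against nearly all under the single-month rule. Because confirmation leaves part of the artefact, change 2 should carry the interpretation.

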9.5.2 Analyses of Secondary Efficacy Endpoint(s)

For continuous secondary efficacy endpoints, summary statistics and primary analysis method will be conducted in the same way as that for the primary endpoints as specified in [Section 9.5.1](#).

For dichotomous secondary endpoints, comparison between treatment arms will be performed using a stratified CMH test for the primary analysis. Sensitivity analyses will use generalized linear mixed effects model on observed data, adjusting for baseline values and stratification factors with appropriate contrasts for pairwise comparisons. The odds ratio for each AMG 301 treatment group versus placebo group, associated 95% confidence intervals, and unadjusted p-values will be reported. Sensitivity analyses for response include: a logistic regression model using data through week 12, adjusting for baseline values where missing values will be imputed as non-responders.

Subgroup analyses are performed for secondary efficacy endpoints using the same method as primary analysis method but performed within each interested subgroup. The treatment difference (or odds ratio) with associated 95% confidence interval and p-values will be reported within each subgroup.

CCI

A large black rectangular box redacting content. The text 'CCI' is visible in the top-left corner of the redacted area.

9.5.4 Analyses of Clinical Outcome Assessments (COAs) and Patient Reported Outcomes (PROs)

The COAs and PROs include MPFID, HIT-6, MMIDAS and CAPS. Change from baseline in total score (or subscale if applicable) of each COA and PRO (except endpoints described in the [Section 9.5.1](#) above) will be reported during the DBTP.

For HIT-6, in addition to the analysis of continuous change from baseline value, proportions of subject with a \geq 5-point reduction from baseline and proportions of subject with HIT-6 \geq 60 (severe impact) will be analyzed similarly as the primary analysis method for dichotomous efficacy endpoints described in [Section 9.5.2](#) above. No sensitivity analysis will be conducted for COA and PROs except for MPFID. The PAS will be used to analyze COA and PRO endpoints.

Table 9-2. Summary of COA and PRO Endpoints and Analysis Methods

Endpoint	Primary Summary and Analysis Method
Change from baseline in the daily activity impact of a headache as measured by the HIT-6 total score	1. Summary statistics by visit using observed data 2. Least squares mean at each time point calculated based on a linear mixed effects model including treatment group, baseline value, stratification factors, scheduled visit, and the interaction of treatment group with scheduled visit, without any subject-level imputation for missing data.
Change from baseline in CAPS	Same as above
Change from baseline in migraine-related disability and productivity as measured by the modified MIDAS (Note: MIDAS scores are collected every month. The first post-baseline measurement of the modified MIDAS scores are at week 4)	Same as above; using ANCOVA model instead of generalized linear mixed effect model.
Change from baseline in monthly mean overall impact on everyday activities score as measured by MPFID stand-alone item	Same as above; using ANCOVA model instead of generalized linear mixed effects model.
Change from baseline in monthly days with physical impairment as measured by MPFID	Same as above; using ANCOVA model instead of generalized linear mixed effects model.
HIT-6 severity grade shift from baseline	Summary statistics for DBTP only. Shift table will also be provided to compare baseline values vs the most extreme post-baseline values through the DBTP.
MMIDAS severity grade shift from baseline	Summary statistics for DBTP only. Shift table will also be provided to compare baseline values vs the most extreme post-baseline values through the DBTP.

9.5.5 Pharmacokinetic Endpoints

AMG 301 exposure parameters of mean concentration over the DBTP will be estimated.

9.6 Safety Analyses

9.6.1 Analyses of Primary Safety Endpoint(s)

For safety endpoints, all randomized subjects who received at least one dose of IP (ie, SAS) will be analyzed based on the randomized treatment unless a subject has received the incorrect dose during the entire DBTP.

No statistical testing comparing treatment groups will be performed in the safety analyses.

Table 9-3. Safety Endpoint Summary Table

Endpoint	Primary Summary and Analysis Method (Specify Analysis Set if FAS is Not Used)
Secondary	
For safety endpoints, data for all enrolled subjects who received at least 1 dose of investigational product (ie, SAS) will be analyzed based on the randomized treatment unless a subject has received the incorrect dose the entire period of interest (period or study).
 
The Medical Dictionary for Regulatory Activities (MedDRA) version 21.1 or later will be used to code all adverse events to a system organ class and a preferred term. All adverse events will be graded using the CTCAE Version 4 as described in Appendix 4 of the protocol. All adverse event tables will be summarized by treatment group.
 
Subject incidence of adverse events will be summarized for all treatment-emergent adverse events, serious adverse events, adverse events leading to withdrawal of investigational product, and fatal adverse events. Adverse events will be tabulated by system organ class and preferred term in alphabetical order.
 
In addition, subject incidence of all treatment-emergent adverse events and serious adverse events will be tabulated by system organ class, preferred term and CTCAE grade in alphabetical order. Subject incidence of all treatment-emergent adverse events and serious adverse events will also be tabulated by preferred term in descending order of frequency.
 
No statistical testing comparing treatment groups will be performed for the safety analyses. Descriptive statistics will be provided for all safety endpoints.

